1.4. Schedule of Assessments

The schedule of assessments is presented in Schedule of Assessments

Dispense Electronic Diary ^J	X															
Corticosteroid Dosing Taper (if applicable) ^K				X		X	X	X								
Telephone Call ^L					X											
Concomitant Medications	-----X-----															
Adverse Event Assessment ^M	-----X-----															
Laboratory Assessments																
Pregnancy Test (females of childbearing potential only) ^N	X		X	X	X		X	X	X	X	X	X	X	X	X	X
FSH ^O	X															
Chemistry, Hematology	X		X	X	X		X		X	X	X	X	X	X	X	X
Urinalysis	X		X	X	X		X		X	X	X	X	X	X	X	X
Overnight Fasting Lipid Panel		X ^P	X	X	X		X		X	X	X	X	X	X	X	X
Viral hepatitis and HIV Serology Panel	X ^Q															
██████████ ██████████		■ ^R	■	■	■		■		■	■	■	■	■	■	■	■
Tuberculosis Test (QuantiFeron)	X															
Ileocolonoscopy and Biopsies		X ^R					X ^C									
Fecal Sample for Infectious Studies ^S	X															
██████████ ██████████ ██████████			■ ^R				■ ^R				■ ^R		■ ^R		■ ^R	

██████████ ██████████			■	■	■		■	■	■	■		■				
██████████ ██████████ ██████████		■	■	■	■		■	■	■	■		■		■	■	■
Genetic Blood Sample (Optional – only collected for subjects who provide genetic testing consent)			X													
Disease Assessments																
CDAI Score		X ^v	X	X	X		X		X		X	X		X	X	X ^A
██████████ ██████████		■	■	■	■		■		■	■	■	■		■	■	■
SES-CD Score		X					X									
Fistula Drainage Status (yes/no to active drainage), if fistula is present	X		X	X	X		X					X		X	X	X
██████████			■				■				■	■		■	■	
██████████			■				■				■	■		■	■	
Subject Diary Completion and Compliance Review ^J	X	X	X ^w	X	X		X	X	X	X	X	X	X	X	X	X ^A

Abbreviations: ECG, electrocardiogram; FSH, follicle stimulating hormone; ██████████; ██████████; ██████████; CDAI, Crohn’s Disease Activity Index; SES-CD, Simplified Endoscopy Score; ██████████; EOS, End-of Study, ATE, Active Treatment Extension

A. This visit is for subjects who prematurely discontinue the study drug. This visit will be conducted within 5 days of the last dose of study drug, if possible. Subject will also return for the EOS visit for collection of safety data and assessment of disease activity. Subjects who discontinue study drug early due to AE are permitted to optionally complete their daily diary through to the EOS visit. Subjects who have not shown clinical improvement at ATE Week 16 should complete an Early Study Drug Discontinuation visit and be discontinued from study drug.

- B. An EOS visit will be required for all subjects 4 weeks following their last dose of study drug, whether they completed the full duration of study drug treatment.
- C. The Week 12 ileocolonoscopy and biopsies should be performed on the same day as the Week 12 visit, preferably in the early morning, to permit morning dosing with study drug. However, if not feasible to perform both the ileocolonoscopy and the clinic visit on the same day, the ileocolonoscopy could be performed within 3 days after the Week 12 clinic visit. If the study activities of this Week 12 visit are to be completed over two different visits, the study drug should be continued until the later of the two visits. The Week 12 endoscopy must be performed at least 1 day prior to ATE Day 1.
- D. ATE Day 1 should occur between 1 and 7 days after the Week 12 clinic visit. No new study drug will be dispensed between the Week 12 clinic visit and ATE Day 1. ATE Day 1 must be performed at least 1 day after the Week 12 endoscopy has been conducted.
- E. Subjects who have not shown clinical improvement, as deemed by the subject and investigator, 16 weeks after initiation of the ATE (i.e., ATE Week 16), should be discontinued from the study.
- F. Physical exams (PEs) should be performed as per local standard practice.
- G. Subjects who have had a documented chest X-ray or equivalent chest imaging or TB testing within 90 days prior to Screening do not require a repeat X-ray (or equivalent) or TB testing, respectively, unless subject is deemed by the investigator to be at high risk of recent pulmonary infection. If a chest X-ray is indicated, it may be performed anytime during Screening. Subjects with a history of latent TB should not have a TB test but must not live in a region with high prevalence of multidrug-resistant TB and have completed a well-accepted treatment regimen (e.g., a ≥ 9-month course of INH or equivalent therapy) within 5 years (3 years in countries where TB is endemic) prior to Screening, the documentation for which must be included in the source document and reviewed by the PI. Subjects who had treated active TB must still have a TB test. Subjects who has a history of latent or active tuberculosis (TB) may be eligible for the study if criteria are met.
- H. Subject will be randomized on Day 1 after all pre-dose procedures (ECG, vital signs, and all labs [REDACTED]) have been completed and subject is confirmed to be eligible for the study.
- I. Study drug administration will be in clinic on Day 1, Week 4, Week 8, Week 12, ATE Day 1, ATE Week 4, ATE Week 8, ATE Week 16, ATE Week 24, ATE Week 36, and ATE Week 48 on an empty stomach from the night before after all pre-dose assessments (with the exception of [REDACTED], which may be done post-visit on the same day) and procedures have been completed. Subject will take the study drug at home for the rest of the study. The last dose of Induction study drug will be taken at the Week 12 clinic visit. No new study drug will be dispensed between the Week 12 clinic visit and ATE Day 1.
- J. Subjects will be provided with an electronic diary (or paper diary if electronic diary is not available) at the Screening Stage 1 visit and instructed on daily diary completion, including symptom monitoring and study drug dosing details. Diaries of symptoms will be collected daily from the Screening Stage 1 visit through the EOS visit. Study drug dosing details will be entered from Day 1 (Induction) through ATE Week 48 (or the last dose of study drug, if the subject prematurely withdraws from study drug). Diary completion will be monitored for completeness at each return study visit after the electronic diary is dispensed (i.e., Screening Stage 2 through the EOS visit). Subjects will be counseled on missed study drug doses and missed diary entries.
- K. Corticosteroid taper, for those that are on corticosteroid at Screening Stage 1, should be initiated at the Week 8 visit.
- L. Site personnel to call subjects approximately 2 weeks prior to Week 12 visit for reminder of compliance of diary completion. The site will also review compliance on corticosteroid taper (as applicable), review upcoming schedule for Week 12 and the reminders in preparation for the visit.
- M. AE assessments are to include collection and reporting of AEs, SAEs, and AEs of Special Interest (AESIs).
- N. Urine beta human chorionic gonadotropin (b-hCG) testing will be performed before dosing when dosing in-clinic and anytime during all other visits for females of childbearing potential to confirm absence of pregnancy. If urine b-hCG test is positive, confirm with serum b-hCG test.
- O. Required for postmenopausal females.
- P. Any Screening Stage 2 lab testing can be obtained from Day -35* to Day -1 during Screening. Overnight fasting lipid panel may be obtained on Day -35 if subjects are fasting as per institutions standard of care procedure, which must be clearly documented in the source documents. ***NOTE: Subjects must not**

be requested to come in fasting for study specific assessments prior to signing the informed consent. Results of these labs will not need to be reviewed before Screening Stage 2 or Day 1.

- Q. Subjects with positive hepatitis B core antibody will undergo testing for hepatitis B DNA and hepatitis B surface antibody during Screening. Subjects with known hepatitis C will also undergo testing for hepatitis C RNA viral load (for details on Serology testing). During re-screening, if there is already a negative result from prior screening, the hepatitis B, C, or E or HIV serologies do not need to be repeated.
- R. Ileocolonoscopy and biopsies will be performed after subject's eligibility is confirmed (upon review of CDAI score prior to the start of bowel preparation and no exclusionary criteria are met). Ileocolonoscopy does not need to be repeated for a rescreening if the ileocolonoscopy is within 28 days of Day 1 of the re-screen and if the SES-CD score is qualifying.
- S. Stool infectious studies to include: C. difficile, other bacteria (including Shigella, Salmonella, Yersinia, Enterohemorrhagic or Enteropathogenic or Enterohemorrhagic E. coli O157, and Campylobacter), and ova and parasite.

T. [REDACTED]

[REDACTED]

[REDACTED]

[REDACTED]

[REDACTED]

[REDACTED]

[REDACTED]

[REDACTED]

[REDACTED]

[REDACTED]

[REDACTED]

[REDACTED]

- V. Obtained prior to ileocolonoscopy (to assess eligibility criteria at Screening). Any time after Screening Stage 1 and once a minimum of 5 entries have been confirmed, the clinician assessments can be completed. Should be performed prior to the start of bowel preparation for the Screening Stage 2 endoscopy. The Screening Stage 1 weight and hematocrit result will be used to calculate this CDAI score.

W. Subject must have completed their electronic diary (or paper diary if electronic diary is not available) at least 5 out of 7 days prior to Screening Stage 2.

1.5. Sample Size Determination

Assuming that the less effective TD-1473 dose results in a 45-point improvement in placebo-adjusted CDAI change from baseline at Week 12, the more effective dose results in a 60-point improvement, and the residual SD is 100 points, 100,000 simulations performed using SAS/IML software yielded the following power estimates for 2-sided testing with the family-wise type 1 error rate for the primary efficacy endpoint controlled at 5% using the Hochberg step-up procedure¹:

- 82% power to show at least one of the two doses effective
- 58% power to show both doses effective

A more detailed rationale, including the basis for estimating the SD of CDAI change as 100 points, is given in “TD-1473 Study 0173 Sample Size Determination v1.0”

¹ The Hochberg step-up procedure is as follows: if both TD-1473 doses vs placebo p-values are $< .05$, reject both no-effect null hypotheses; otherwise, if the smaller p-value is $< .025$, reject the no-effect null hypothesis for that dose.

2. ANALYSIS SETS

Table 5: Analysis Sets

Analysis Set	Definition	Treatment Assignment
Screen Failures*	Subjects who give informed written consent but are not randomized are considered screen failures. Screen failure subjects and the main reason for screen fail will be captured in the EDC.	N/A
Randomized*	The randomized analysis set will include all subjects who were randomized into the study.	Randomized treatment
Safety*	The Safety analysis set will include all subjects who received at least one dose of study drug (or placebo). The Safety analysis set is the primary analysis set for safety analyses.	Actual Treatment received (see Section 3.1.6)
ITT*	The Intent-to-Treat (ITT) analysis set comprises all randomized subjects who receive at least one dose of study drug.	Randomized treatment
Modified ITT*	The modified Intent-to-Treat (mITT) analysis set comprises all randomized subjects who receive at least one dose of study drug and have at least one postbaseline CDAI score. Only include subjects randomized prior to the 23Aug2021. The mITT set is the primary analysis set for efficacy summaries and analyses.	Randomized treatment
PP*	The Per-Protocol (PP) analysis set comprises all subjects in the mITT analysis set who complete their Week 12 visit and have no major analysis protocol deviations	Randomized treatment
Active Draining Fistulae*	The active draining fistulae analysis set comprises all subjects in the mITT analysis set with at least one draining fistula at baseline.	Randomized treatment

* Due to confirmed data integrity violations the data for site 36016 (deviation report GCP-XX) and site 38915 (deviation report GCP-11) will be excluded from all analysis sets.

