8.9. Handling of Missing Data

For the primary analysis of score change endpoints (e.g., CDAI score change, SES-CD score change), missing values will not be imputed. Sensitivity analyses for the primary endpoint will be specified in the SAP, and will be performed if one or both TD-1473 doses are shown to reduce Week 12 CDAI more than placebo.

Subjects with missing data for binary efficacy endpoints will be counted as treatment failures. Alternative approaches may be specified in the SAP.

In addition, subjects who had nonmissing data for a binary efficacy endpoint meeting the criterion for success but met one of the following criteria prior to the visit will be counted as treatment failures:

- Received rescue medication, defined as any medication given to treat CD symptoms, other than antidiarrheal medication for control of chronic diarrhea, if started postbaseline or if the dose was increased postbaseline to a dose higher than at baseline (both induction and ATE; ATE baseline is Week 12)
- Experienced disease worsening, defined as an increase in CDAI score from baseline of ≥ 100 points at consecutive visits (ATE only; ATE baseline is Week 12)

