3.4.4. Secondary Efficacy Analyses

3.4.4.1. Estimands

The treatment policy strategy that was used for the primary estimand for the primary endpoint analysis will be used for change from baseline in SES-CD Score at Week 12.

The remaining secondary endpoints of response/remission will be analyzed through a composite strategy as follows:

- Population: Same as primary estimand
- Variable: Endpoints(Section 3.4.1) and Definition (3.4.3)
- Intercurrent Events: For this estimand, meeting the criteria of an ICE (1-5) is considered an unfavorable outcome and subjects who meet these criteria prior to Week 12 will be considered not to be in response/remission.

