3.4.4.2. Analysis Methods

The proportion of subjects at Week 12 with CDAI clinical response, CDAI clinical remission, Endoscopic Response and SFAP clinical remission will be analyzed separately using a stratified Cochran-Mantel-Haenszel (CMH) test, stratifying by prior biologic status (yes, no) and CDAI baseline score category (≤ 300 , >300) as determined from information in the clinical database. Summaries of the proportion of subjects in response/remission will be presented by treatment group, the adjusted treatment difference in proportions between each TD-1473 and placebo will also be presented along with associated 95% CIs calculated based on the Wald method. P-values from the CMH Chi-square test for the comparison of each dose of TD-1473 versus placebo will also be presented.

Separate 2-group forest plots for the difference in proportion of each secondary endpoint of response/remission versus placebo at Week 12 will display the CMH weighted difference in proportions and associated 95% CI.

Analysis of change from baseline in SES-CD at Week 12 will be performed using an ANCOVA model. The model will include independent fixed-effect class terms for treatment group, prior biologic failure status (yes, no) and CDAI baseline score category (≤ 300 , >300) with baseline SES-CD as a covariate.

Summaries will be on the mITT population and include observed values, change from baseline values and least square (LS) means estimates. Each TD-1473 dose versus placebo will be compared by displaying the LS mean difference estimate to placebo and associated 95% confidence interval. Nominal p-values will also be reported.

A 3-group forest plot will summarize the LS mean change from baseline in SES-CD at Week 12 with 95% confidence interval.

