3.4.4.3. Missing Data Handling

For change in SES-CD at Week 12, missing data will be assumed MCAR there will be no imputation of missing data.

For binary endpoints missing data will be imputed with non-responder imputation with the exception of data missing due to COVID-19, in these instances the data will be assumed missing completely at random and not analyzed.

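### The responder endpoints are analysed in an mITT set that leaves out dosed subjects with no postbaseline CDAI, so the rules that count missing outcomes as failures cannot reach them

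*SAP*

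**What the plan says.** SAP section 2 (Table 5) admits to mITT only randomized, dosed subjects who "have at least one postbaseline CDAI score" and who were randomized before 23Aug2021. It adds: "The mITT set is the primary analysis set for efficacy summaries and analyses". Protocol 8.3 has the same CDAI condition and the same primary role for mITT. SAP 3.4.4.2, on the secondary endpoints, names no other set: "Summaries will be on the mITT population and include observed values, change from baseline values and least square (LS) means estimates".

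The failure rules are separate. Protocol 8.9: "Subjects with missing data for binary efficacy endpoints will be counted as treatment failures". SAP 3.4.4.3: "For binary endpoints missing data will be imputed with non-responder imputation with the exception of data missing due to COVID-19". SAP 3.4.4.1 adds a composite rule for intercurrent events 1-5, one of which is stopping study drug for worsening Crohn's disease or lack of benefit: "subjects who meet these criteria prior to Week 12 will be considered not to be in response/remission".

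Table 5 also defines a wider set: "The Intent-to-Treat (ITT) analysis set comprises all randomized subjects who receive at least one dose of study drug". SAP 3.2 uses it for study-population summaries. SAP 3.4.5 plans no sensitivity analysis for the secondary endpoints.

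**The concern.** Failure imputation needs no postbaseline data, so a responder analysis has no technical reason to require any. The repeated-measures model for CDAI change is different, because a subject without a postbaseline value adds nothing to it. Carrying the same set over to the binary endpoints makes entry depend on something that happens after randomization. Endoscopic response is scored on SES-CD, yet entry to its analysis still depends on CDAI. A subject who stops early for lack of benefit and has no later CDAI meets the estimand's own definition of failure but is not counted as one.

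At stake are the response and remission rates and their differences from placebo. Protocol 3.5.2 says the induction analysis will inform the design of further studies, so these estimates will be used even though they are not formally tested.

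**Working it through.** **Who is outside mITT**

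- Protocol 6.3.15 asks subjects who stop study drug early, for any reason other than withdrawal of consent, to return within 5 days of the last dose if possible. CDAI components are collected then, and again at the End of Study visit 4 weeks after the last dose (Protocol 6.3.14).
- SAP 3.3.2 needs only 4 available subscores for a CDAI score, with the others carried forward.
- Broad reading: Table 5 names no visit window, so any such score qualifies. The losses are then mainly consent withdrawals, subjects lost to follow-up and subjects who attend neither visit.
- Narrow reading: SAP 3.1 restricts analyses and derived parameters to scheduled or windowed data unless noted otherwise. In SAP 3.1.3 the first postbaseline window opens on Induction Day 21, and anything outside a window is treated as unscheduled whatever its label. SAP 3.1.5.1 also ends induction data at last dose plus 5 days, which would shut out the End of Study score. On this reading a subject who leaves before Day 21 may have no qualifying CDAI even after attending both visits.
- The SAP does not say which reading applies.

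**Effect on the rates**

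The documents give no figure for this point. Their 82% and 58% power concern mean CDAI change and do not bear on it. Arm sizes of 60 per dose and 40 on placebo come from Protocol 8.2. Responder counts and early losses are assumptions. For scale, the losses tried run from 0 to 10% of an arm. The 10% is borrowed from the replacement trigger in Protocol 6.5.2, which is not a forecast of dropout.

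With r responders among n dosed subjects, d of whom have no postbaseline CDAI, the rate is r/n if all are kept and r/(n − d) in mITT. Because r is unchanged, each arm's rate can only rise.

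Assume 18/60 active and 8/40 placebo. With everyone kept, the difference is 30.0% − 20.0% = 10.0 points.

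| Lost, active / placebo | Active | Placebo | Difference (points) |
|---|---|---|---|
| 3 / 2 (5% each) | 18/57 = 31.6% | 8/38 = 21.1% | 10.5 |
| 3 / 1 | 18/57 = 31.6% | 8/39 = 20.5% | 11.1 |
| 5 / 2 | 18/55 = 32.7% | 8/38 = 21.1% | 11.7 |
| 6 / 1 | 18/54 = 33.3% | 8/39 = 20.5% | 12.8 |
| 1 / 3 | 18/59 = 30.5% | 8/37 = 21.6% | 8.9 |
| 0 / 4 | 18/60 = 30.0% | 8/36 = 22.2% | 7.8 |

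These are illustrations, not bounds: losing 6 active and no placebo subjects would give 18/54 − 8/40 = 13.3 points. If both arms lose the same fraction l, the difference is multiplied by 1/(1 − l); for 5%, 10.0/0.95 = 10.5.

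The standard error of the difference with all kept is √(0.3 × 0.7/60 + 0.2 × 0.8/40) = √0.0075, or 8.7 points. The tabulated shifts of −2.2 to +2.8 points are at most about 0.3 of that.

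A second assumed case, 30/60 against 12/40, starts at 20.0 points (unstratified pooled z test, p = 0.047). Losing 6 active and no placebo subjects gives 30/54 − 12/40 = 25.6 points (p = 0.014). Losing no active and 4 placebo subjects gives 30/60 − 12/36 = 16.7 points (p = 0.11). The planned test is a stratified CMH, so these p-values are only indicative.

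**The case against.** The best defence is that the gap is narrow and was specified in advance. The protocol defines the same mITT, so this is a consistent choice and not a late SAP change. The discontinuation and End of Study visits can keep many early leavers in the set. Non-responder imputation still covers every mITT subject missing at Week 12 for reasons other than COVID-19. The endpoints are unpowered and carry nominal p-values. SAP 3.2.1 reports discontinuations before Week 12 with reasons, and lists analysis-set flags by subject, so the excluded subjects can be identified. All of this stands and limits the weight of the point. It does not put the excluded subjects back into the denominator.

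A reader might infer three stronger things that the documents do not support:

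- That everyone who leaves before Week 4 is lost. Table 5 asks for any postbaseline CDAI, and two later visits collect one.
- That the rule counting missing as failure is defeated altogether. It fails only for subjects with no postbaseline score.
- That the difference is inflated in favour of TD-1473. That needs proportionately heavier, or at least similar, early loss on active treatment; with enough extra loss on placebo the difference shrinks.

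**Conclusion.** The mechanism holds on the documents' own wording: dosed subjects with no postbaseline CDAI drop out of the responder analyses before any failure rule applies, and no planned analysis shows the effect. Each arm's rate is biased upward. The bias in the difference has unknown sign and size, because neither the number without a postbaseline CDAI nor the responder rates are given. Under the assumed 18/60 against 8/40, the tabulated cases move 10.0 points to between 7.8 and 12.8, which is small beside the sampling error. The primary MMRM conclusion is untouched by this route. The point merits correction because the change needs no new data. Separately, the SAP should settle whether an early discontinuation score confers mITT membership, since that also decides who belongs to the primary efficacy set.

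**What to change.** - In SAP 3.4.4.2, name all randomized and dosed subjects (the SAP's ITT set) as the analysis set for the binary endpoints. Count those without postbaseline data as non-responders and leave the COVID-19 rule as it stands.
- Apply the same site exclusions and 23Aug2021 cut-off as mITT. The site exclusions already cover every set, but the cut-off is written only in the mITT row, so ITT as it stands would readmit later-randomized subjects.
- Record the departure from Protocol 8.3 in SAP 5.1.
- Keep the mITT version as a sensitivity analysis and amend SAP 3.4.5 to say so.
- State in Table 5 whether a CDAI from the discontinuation visit, including one before Induction Day 21, qualifies a subject for mITT.
- Leave the primary MMRM set otherwise unchanged.

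The cost is edits in a few places rather than one line, slightly lower reported response rates, and one extra set of tables.

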6.5.2. Subject Replacement

At the Sponsor's discretion, subjects who withdraw or are withdrawn before taking study drug may be replaced. Should greater than 10% of treated patients withdraw before the primary endpoint visit or miss the primary endpoint visit due to events that could not be foreseen during study design planning (e.g., COVID-19 pandemic) then treated subjects may be replaced. Safety data will be presented for all subjects in the Clinical Study Report (CSR) regardless of whether the subject was a replacement.

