8. STATISTICAL CONSIDERATIONS

8.1. General Considerations

All data for each subject will be listed as collected. All statistical summaries and analyses will be performed using [REDACTED]

Continuous data will be summarized using an 8-point summary (n, mean, standard deviation [SD], median, interquartile range [25% quartile, 75% quartile], minimum, and maximum) unless otherwise specified in the SAP or table shell. Categorical data will be summarized using counts and percentages.

Study Day 1 is defined as the day of the first study drug dose. The preceding day is Study Day -1.

Baseline is the last assessment (scheduled or unscheduled) obtained before start of study drug dosing, unless otherwise specified in the SAP (e.g., for fecal sample assessments). Baseline for endpoints that have more than one component is calculated from the individual component baselines, whether or not they were assessed during the same visit.

The study will include 2 formal database locks, one after all 160 subjects have either completed or withdrawn from the Induction phase, and one after all subjects have completed or withdrawn from the ATE phase. Separate SAPs will be prepared for the following unblinded analyses, and finalized before the database are locked for analysis:

Database lock after the Induction Phase is completed:

- Analyses of induction data, to include specifications for [REDACTED] [REDACTED] SAP, when not otherwise specified, refers to this SAP)

- [REDACTED]

- [REDACTED]

Database lock after the ATE phase is completed:

- Analyses of ATE data

Any changes to the data summaries and analyses outlined in this section will be described in the applicable SAP. Any major changes to the definition of the primary endpoint will also be included in a protocol amendment.

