8.3. Analysis Sets

The modified Intent-to-Treat (mITT) analysis set comprises all randomized subjects who receive at least one dose of study drug and have at least one postbaseline CDAI score. The mITT set is the primary analysis set for efficacy summaries and analyses.

The Per-Protocol (PP) analysis set comprises all subjects in the mITT analysis set with no major analysis protocol deviations (Section 8.3.2). If the number of mITT subjects excluded from the PP analysis set is ≤ 5 per treatment group, PP analyses will not be performed. Otherwise, both the mITT and the PP analysis set will be used for selected efficacy summaries and analyses.

The Safety analysis set comprises all subjects who receive at least one dose of study drug. The Safety analysis set will be the analysis set for both general (baseline, exposure, and compliance) and safety analyses.

[REDACTED]

Except for the [REDACTED] Analyses using the mITT analysis set will be by randomized treatment. Analyses using the PP analysis set and the Safety analysis set will be by actual treatment.

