3. STATISTICAL ANALYSES

3.1. General Considerations

All data from scheduled and unscheduled visits will be presented in the subject listings.

However, unless noted otherwise, only data from scheduled/windowed visits will be included in the summaries, statistical analysis, and calculation of derived parameters.

Summary tables and listings (e.g., post text tables and individual subject data listings are prepared according to ICH Guideline E3) include a “footer” providing explanatory notes.

Continuous variables will be summarized using an 8-point descriptive summary (number of subjects [n], mean, standard deviation [SD], median [Q2], interquartile range [25th percentile Q1, 75th percentile Q3], minimum, and maximum) unless otherwise indicated. Categorical variables will be summarized by frequency and percentage of subjects in each category. All summaries will be presented by treatment and visit when applicable.

For binary endpoint comparisons to placebo when the expected number of responders/non-responders are less than 5 per treatment groups being analyzed a fishers exact test will be performed. For safety assessments, summary statistics will be reported by treatment.

Analyses and tabulations will generally be prepared using SAS®, version 9.4 or later.

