3.2.3. Protocol Deviations

Unique subjects reporting major protocol deviations that have significant impact on primary efficacy analyses (major analysis protocol deviations) will be summarized overall and by treatment group for the ITT set.

[REDACTED]

[REDACTED]

[REDACTED]

[REDACTED]

[REDACTED]

■ [REDACTED]

[REDACTED]

[REDACTED]

■ [REDACTED]

■ [REDACTED]

A subject listing with all protocol deviations identified prior to database lock will be provided. Moreover, a listing of all major analysis protocol deviations will be provided. All subject listings will be based on the randomized analysis set.

A summary and listing of COVID-19 protocol deviations will also be presented, along with a listing of COVID-19 impacts.

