3.7. Safety Analyses

The analysis of safety and tolerability data includes an overall summary of tolerability, adverse event preferred terms by body/organ system, drug exposure (duration of treatment), dosing information/compliance clinical laboratory results, vital signs and ECGs. Tables summarizing the adverse events reported by subjects who died, experienced non-fatal serious adverse events (SAE), or prematurely discontinued the study due to adverse event (AEs) will be prepared.

In general, inferential statistical tests are not performed for adverse event incidence rates.

For all safety analyses, the safety analysis population will be used.

For summaries on exposure, compliance and adverse events for the study overall (Induction and ATE),

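### Any subjects dosed at the two excluded sites would be absent from the safety tables, and the readable SAP plans no labelled all-dosed display

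*SAP*

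**What the plan says.** **Exclusion.** The footnote to the analysis-set table in SAP section 2 states that data from sites 36016 and 38915 "will be excluded from all analysis sets". The reason given is data integrity violations, described as confirmed. All seven rows are starred: Screen Failures, Randomized, Safety, ITT, modified ITT, PP and Active Draining Fistulae.

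**Safety tables.** SAP 3.7: "For all safety analyses, the safety analysis population will be used". Exposure (3.7.1), adverse events including SAEs, deaths and discontinuations (3.7.2) and AESIs (3.7.2.1) all fall under this rule.

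**Disposition.** SAP 3.2 makes ITT the default set for study-population summaries. SAP 3.2.1 plans counts of subjects screened, randomized and treated. It also plans a disposition listing with analysis-set flags and dates of first and last dose.

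**Listings.** SAP 3.1: "All data from scheduled and unscheduled visits will be presented in the subject listings". SAP 3.7.2 plans listings of all AEs and SAEs. SAP 3.2.3, on protocol deviations, says: "All subject listings will be based on the randomized analysis set".

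**Protocol.** Section 8.3: "The Safety analysis set comprises all subjects who receive at least one dose of study drug". It names no site exclusion. Section 8.1: "Any changes to the data summaries and analyses outlined in this section will be described in the applicable SAP". Section 6.5.2, on replacements: "Safety data will be presented for all subjects in the Clinical Study Report (CSR) regardless of whether the subject was a replacement".

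**The concern.** Safety and tolerability is one of the two primary objectives (SAP 1.1.1, protocol section 2). A finding that a site's data cannot be trusted is a sound reason to keep its CDAI and endoscopy scores out of the efficacy comparison. It does not by itself show that nobody there took study drug or had a serious event.

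If the tables follow the footnote as written, a reader of the safety section would see denominators and event counts for a subset of the dosed subjects. Nothing in the summary tables would tell that reader how many dosed subjects were left out, from which arms, or whether the safety picture changes when they are put back. With planned arms of 60, 60 and 40, one subject with a serious event is visible in a rate.

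**Working it through.** The documents contain no figure on this point to reproduce. The check is to trace each planned output to its analysis set.

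| Output | Set used | Source | Starred? |
|---|---|---|---|
| Exposure, AEs, SAEs, deaths, discontinuations, AESIs | Safety | SAP 3.7 | Yes |
| Disposition: treated | ITT by default | SAP 3.2, 3.2.1 | Yes |
| Disposition: randomized | Not ITT, which requires dosing; Randomized is the natural source | Inference from SAP 2 and 3.2.1 | Yes |
| Disposition: screened | No set named | SAP 3.2.1 | Open |
| Deviation listings | Randomized | SAP 3.2.3 | Yes |
| AE, SAE and disposition listings | No set named, unless the SAP 3.2.3 sentence applies generally | SAP 3.1, 3.2.1, 3.7.2 | Open |

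The first row needs no inference. The treated count follows from the ITT default and the randomized count is very likely. The screened count and the non-deviation listings cannot be settled from the text.

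Next, whether anything makes up for the exclusion. The readable SAP describes no all-dosed table and no separate account of the two sites. Two limits apply: parts of the SAP are redacted, and SAP 3.7 breaks off mid-sentence where it turns to exposure, compliance and AE summaries for the overall study. SAP 5.1, the place for changes to protocol-planned analyses, shows a heading and no text.

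**Illustration of scale (assumed inputs).** The number of subjects at the two sites is not given. Let an arm have n subjects, e of them with an SAE; remove k subjects, x of whom had an SAE. The rate before is e/n and after is (e − x)/(n − k). The n values are the planned arm sizes, which may not apply because the study was terminated early (SAP section 1); e, k and x are assumptions.

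| Arm | Before | k | x = 1 | x = 0 |
|---|---|---|---|---|
| Active, n = 60, e = 4 | 4/60 = 6.7% | 2 | 3/58 = 5.2% | 4/58 = 6.9% |
| | | 5 | 3/55 = 5.5% | 4/55 = 7.3% |
| Placebo, n = 40, e = 3 | 3/40 = 7.5% | 2 | 2/38 = 5.3% | 3/38 = 7.9% |
| | | 5 | 2/35 = 5.7% | 3/35 = 8.6% |

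These shifts run from −2.2 to +1.1 points, but only because x was held to 0 or 1. With x = 2 and k = 2 in placebo, the rate falls to 1/38 = 2.6%, a shift of −4.9 points. With k = 0 nothing changes.

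A second view: suppose m of 160 dosed subjects were at the two sites and 3 subjects in the whole study had some rare event, spread evenly over subjects. The chance that at least one of the 3 drops out of the tables is 1 − [(160 − m)(159 − m)(158 − m)]/(160 × 159 × 158). For m = 4, 8, 16 and 24 this gives 7.4%, 14.3%, 27.3% and 38.8%.

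**The case against.** The strongest reply is that this is a declared analysis choice. The asterisk sits on the Safety row, so the footnote is part of that definition, and protocol 8.1 leaves such changes to the SAP. That stands. A reader might infer that the SAP contradicts itself because the Safety row speaks of all dosed subjects while the footnote removes some. The documents do not support that: row and footnote read together are one definition, and the departure is from protocol 8.3.

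Second, the nature of the violations is set out in deviation reports that are not available here. If dosing or adverse-event records were what failed, an all-dosed display would rest on unreliable records. This also stands. It is a reason to label the display and keep it supplementary; it is not a reason to omit the number of subjects involved.

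Third, the listings may already show these subjects. The disposition listing with set flags and dose dates could show them as dosed but outside the Safety set, SAP 3.7.2 lists all AEs and SAEs, and protocol 8.8.2 promises a listing for every subject with an SAE. The restriction in SAP 3.2.3 may concern deviation listings only. This narrows the point, since the gap is certain for the summary tables and only possible for the listings. Listings would not repair the rates or the counts.

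Fourth, protocol 6.5.2 was written about replacement subjects and is weak support; the argument does not need it.

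**Conclusion.** The point holds and is worth fixing, with its size unknown. Applied as written, the footnote leaves any subjects dosed at sites 36016 and 38915 out of every safety summary table run on the Safety set, and very likely out of the randomized and treated counts. The readable text supplies no labelled all-dosed view, and the change from protocol 8.3 is not visible in SAP 5.1.

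This rests on two conditions: that someone was dosed at those sites, and that the redacted or cut-off text does not already provide the display. If nobody was dosed there, one sentence saying so closes the point. The rate shifts in the illustration are not estimates and not bounds.

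A reader might go further and infer that serious events have been suppressed. The documents do not support this. They report no event at either site, the 24-hour SAE and AESI reporting of protocol 7.4.3 is untouched, and the by-subject listings may include these subjects. Nor is there a case here against excluding the sites from efficacy.

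**What to change.** - Keep the exclusion for the efficacy sets and, if the sponsor prefers, for the main safety tables.
- Report how many subjects were randomized and dosed at the two sites, by arm, and show them in disposition.
- Add a supplementary display, labelled as including the two sites, of exposure, deaths, SAEs, AESIs and AEs leading to discontinuation for all dosed subjects.
- State that the AE, SAE and disposition listings include these subjects with a flag, and say whether the listing rule in SAP 3.2.3 applies beyond protocol deviations.
- Record the departure from the protocol 8.3 Safety set, with its reason, in SAP 5.1.

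Cost: SAP wording and about ten extra tables (five topics, each for Induction and for the overall study). Some safety data of doubtful quality would be displayed, labelled as such. Treatment, data collection and the primary efficacy analysis do not change.
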